- d A QuantiFERON TB/T-spot or local equivalent will be performed. For the purposes of this study. Additional TB tests could be performed during the course of the study at the discretion of the investigator and according to local practice.
- ^e Chest radiograph will include anterior/posterior or posterior/anterior and lateral views. Historical films obtained or formal reports signed off by radiologist in the 3 months prior to screening are acceptable. Chest X-ray may be substituted by a chest CT or chest MRI, if available within 3 months prior to screening.
- Only for subjects with a positive tuberculosis test (ie, positive or indeterminate QuantiFERON, positive PPD).
- Pharmacokinetic sample will be collected as close to the nominal time points as possible. Study centers should strictly adhere to the tolerance windows outlined in the table below for week 28 through week 30 PK endpoint sample collection.
- h Pharmacokinetic and antidrug antibody samples should be drawn prior to investigational product administration at dosing visits (except 1 hour post week 28 dose pharmacokinetic sample).
- ABP 501 or adalimumab will be administered after all other procedures are completed for each visit. If the subject presents with an infection/adverse event at the dosing visit(s), the administration of investigational product may be delayed up to 5 days. In the case of delayed or missed dose, subsequent doses should be administered according to the original schedule (ie, at the planned time point relative to first dose/day 1). A minimum of 7 days must elapse between administrations of 2 doses.
- Subjects achieving less than PASI 50 response at week 12 visit will be considered non-responders and will be discontinued from the study at week 12. Subjects unable to complete the week 12 visit will be discontinued from the study. These subjects will be asked to complete an End of Study Visit procedures.

Table 1-2. Tolerance Windows for Pharmacokinetic Endpoint Sample Collection

Study Visit	Tolerance Windows ^a	
Week 28 predose	Within 3 hours prior to week 28 investigational product administration	
1 hour post week 28 dose	± 15 minutes	
1 day post week 28 dose	± 5 hours	
3 days post week 28 dose	± 6 hours	
4 days post week 28 dose	± 6 hours	
7 days post week 28 dose	± 6 hours	
11 days post week 28 dose	± 24 hours	
14 days post week 28 dose	± 48 hours	

PK = pharmacokinetic(s).

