a. The week 28 visit and dose should be performed with a window of ± 3 days. Subsequent visits are done in relation to the actual week 28 investigational product dose date (eg, for the 3 days post week 28 dose time point, the PK sample should be collected 3 days after the actual week 28 dose, with a collection window of ± 6 hours).

Clinical Study Protocol: 20200497

Final 1.0 Date: 03 Jun 2021 Page **19** of **87**

2 Introduction

ABP 501 is Amgen's biosimilar product to Humira[®] (adalimumab). ABP 501 is approved in the United States (US) under brand name of AMJEVITA[™] (adalimumab-atto) and approved/marketed in European Union and other countries, as AMGEVITA[®] (adalimumab). [AMGEVITA[®] Summary of Product Characteristics (SmPC), March 2020, AMJEVITA[™] (adalimumab-atto) United States Prescribing Information (USPI), June 2019]. ABP 501 is approved as a 50 mg/mL formulation.

Amgen is now developing a new ABP 501 high concentration (mg/mL) formulation (referred to in this protocol as ABP 501-HCF). The dosage forms, route of administration (subcutaneous [SC]) and dosing regimens for ABP 501-HCF will be the same as those for the approved 50 mg /mL formulation;

ABP 501-HCF has not been approved or marketed anywhere. For specifics related to the minor differences in excipients between ABP 501 formulations and analytical comparability assessment please refer to the ABP 501 Investigator's Brochure.

Note that in this protocol the term "investigational product" refers to both, ABP 501-HCF or adalimumab (mg/mL approved formulation).

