Developing antibody incidence during the Post-randomization Period is defined as the number of subjects in the Safety Analysis Set (SAS) who have a positive result post randomization and have never tested positive (i.e., negative or no results) prior to the first dose of post-randomization IP divided by the number of subjects in the SAS who have at least a result post randomization.

End of Study (EOS) Date

The EOS date is the date recorded on the End of Study page of the CRF.

First Dose Date

It is defined as the date the subject received the first dose of IP.

First Post-randomization Dose Date

It is defined as the date the subject received the first post-randomization dose of IP.

Last Dose Date

It is defined as the date the subject received the last dose of IP.

Last Observation Carried Forward (LOCF)

Protocol Number: 20200497

Date: 10FEB2023 Page 14 of 36

A method of imputation where missing post-baseline data will be imputed by carrying forward the last non-missing post-baseline value for that endpoint. Baseline values will not be carried forward.

Neutralizing ADA Negative Subgroup

Defined as subjects in the subset of Safety Analysis Set (SAS) who have never tested positive (i.e. tested negative or no results) prior to the first dose of post-randomization IP, have at least one neutralizing ADA result post-randomization, and all available post-randomization neutralizing ADA results are negative.

Non Responder Imputation (NRI)

A method of imputation where a subject with missing post-baseline binary response data will be imputed as a non-responder, regardless of the reasons for missing data.

Study Analysis Visit

If more than one actual visit (including the unscheduled visits) falls within the same defined window, the visit closest to the target day with non-missing data will be considered for analysis. If two actual visit dates are at the same distance from the target day, the later visit with non-missing data will be considered for analysis.

For Efficacy, Vital, Safety Lab & PK

					Endpoint	
Study Analysis Visit	Target Day	Study Day	Interval (days)	Efficacy	Vital & Safety Labª	PK
Baseline ^b	1	≤1	NA	Х	Х	Х
Week 2	8	2-21	20		X	
Week 6	36	22-56	35	Χ	X	Χ
Week 12 ^b	78	57-91	35	Χ	X	Χ
Week 16	106	92-119	28	Χ	X	Χ
Week 20	134	120-161	42	Χ	X	Χ
Week 28	190	162-196	35		X	Χ
Week 30	14 days post week 28 dose	197-210	14	Х	Х	
Week 32	218	≥211	NA		Χ	

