^a Safety lab is not scheduled at week 2 and week 16. Laboratory parameters assessment will not be included at these two visits in the output tables.

^b If a subject has laboratory measurements on the same day as the first dose date at week 1/Day 1 or week 12 but at a time after the first dose of IP at week 1/Day 1 or week 12, respectively is administered, the laboratory measurements will not be defined as baseline or week 12, but will be included in consideration for week 6 or 20 measurements, respectively.

Protocol Number: 20200497

Date: 10FEB2023 Page 15 of 36

PK concentrations between Week 28 – Week 30 are summarized by nominal study visit per the following table as listed in the protocol:

Tolerance Windows for Pharmacokinetic Endpoint Sample Collection

Study Visit	Tolerance Windows ^a
Week 28 predose	Within 3 hours prior to week 28 investigational product administration
1 hour post week 28 dose	±15 minutes
1 day post week 28 dose	±5 hours
3 days post week 28 dose	±6 hours
4 days post week 28 dose	±6 hours
7 days post week 28 dose	±6 hours
11 days post week 28 dose	±24 hours
14 days post week 28 dose	±48 hours

^a The week 28 visit and dose should be performed with a window of \pm 3 days. Subsequent visits are done in relation to the actual week 28 investigational product dose date (eg, for the 3 days post week 28 dose timepoint, the PK sample should be collected 3 days after the actual week 28 dose, with a collection window of \pm 6 hours). PK: pharmacokinetic(s)

For ADA

Study Analysis Visit	Target Day	Study Day
Baseline	1	<=1
Week 6	36	<=56
Week 12	78	<=91
Week 16	106	<=119
Week 20	134	<=161
Week 28	190	<=196
Week 30	14 days post week 28 dose	<=210
Week 32	218	<=EOS Visit Date

Study Day

Study day is defined as the number of days from Study Day 1.

Before Study Day 1: Study Day = (Date of assessment – Date of Study Day 1)

Protocol Number: 20200497

Date: 10FEB2023 Page 16 of 36

On or After Study Day 1: Study Day = (Date of assessment – Date of Study Day 1) +1

Therefore, the day prior to Study Day 1 is -1.

Study Day 1

Study day 1 is defined as the first day of IP the subject received (see definition of first

dose date).

Study Period

The following definitions will be used for PK, safety and efficacy analyses.

Lead-in Period

It is defined as the time period from the first dose of IP the subject received (see

definition of first dose date for the subject) until prior to the first post-randomization dose

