9.1 General Considerations

All statistical analyses will be performed using SAS® (Version 9.4 or higher).

Unless otherwise specified, descriptive data summaries will be tabulated by treatment for all endpoints. Categorical data will be summarized using number of subjects, frequency and percentages of subjects falling into each category, with the denominator

Protocol Number: 20200497

Date: 10FEB2023 Page 25 of 36

for percentages being the number of subjects in the analysis sets for each treatment group, unless otherwise noted. Percentages will be rounded to one decimal place except for 100%, which will have no decimal place.

All continuous variables will be summarized using mean, standard deviation, median, minimum, maximum, 25th percentile (Q1), 75th percentile (Q3), and number of subjects with observations. The mean, geometric mean, median, Q1, and Q3 will be presented to one decimal place greater than the original data, standard deviation will be two decimal places greater than the original data, and the minimum and maximum will have the same number of decimal places as the original data.

For PK endpoints, additional precision rules are as follow:

Pharmacokinetic serum concentrations will be reported in ng/ml with 3 decimal places and will follow the general conventions for summary statistics.

Pharmacokinetic parameters with units of ng/ml or h*ng/ml will be converted to ug/ml or h*ug/ml with 1 decimal place.

Summary Statistics	Reporting Precision			
CV%/geometric CV%	1 d.p.			
Geometric LS mean	2 d.p.			
Geometric LS mean ratios	4 d.p.			
CI	Same number of decimal places as the associated statistic			

d.p.= decimal place(s)

Confidence intervals may also be provided (when specified).

For any of the summaries that are to be done by visit, the derived analysis study visit as defined in Section 5.1 will be used for analysis unless otherwise noted.

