9.6.2 Analyses of Secondary Efficacy Endpoint(s)

9.6.2.1 Primary Analysis

The primary analysis will be performed based on the Per-protocol Efficacy Analysis Set according to the actual treatment groups with missing PASI score at Week 30 visit imputed by LOCF and missing PASI 75, PASI 90 and PASI 100 response at week 30 imputed by NRI. Confidence interval for response rates will be calculated by the Clopper-Pearson method.

The point estimate and 90% CI of the mean difference in PASI percent improvement from baseline at Week 30 will be estimated from an ANCOVA model adjusting for the baseline PASI value and the stratification factors.

Protocol Number: 20200497

Date: 10FEB2023 Page 30 of 36

The point estimate and 90% CI of the risk difference in PASI 75, PASI 90, and PASI 100 response rates at Week 30 will be estimated from a generalized linear model with an identity link adjusting for the stratification factors.

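### SAP 5.1 targets the Week 30 efficacy visit from the week-28 dose but windows it on fixed study days, so a week-28 dose on day 195 or later can cost a subject the week-30 PASI

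*SAP*

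**What the plan says.** **Timing in the protocol.** The Schedule of Assessments (Protocol 1.3, Table 1-1) places the week-30 PASI, sPGA and BSA in the +14-day column counted from the actual week-28 dose. Table 1-2 footnote a gives the week-28 visit and dose a window of ±3 days and adds: "Subsequent visits are done in relation to the actual week 28 investigational product dose date". Table 1-2 allows ±48 hours at the +14-day time point; that tolerance is written for PK samples. Table 1-1 footnote i says that, for a subject with an infection or adverse event at a dosing visit, "the administration of investigational product may be delayed up to 5 days". Protocol 6.7 repeats a 5-day limit for serious infection but also withholds product until the infection has resolved.

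**Visit assignment in the SAP.** The SAP 5.1 table has these rows:
- Week 28: "Week 28 190 162-196", not marked for efficacy.
- Week 30: "14 days post week 28 dose 197-210", marked for efficacy.
- Week 32: "Week 32 218 ≥211", not marked for efficacy.

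SAP 9.1 states that for by-visit summaries "the derived analysis study visit as defined in Section 5.1 will be used for analysis unless otherwise noted". The only relevant exception in SAP 5.1 covers PK concentrations between weeks 28 and 30, which are summarised by nominal visit.

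**Missing data.** SAP 9.6.2.1 has a missing week-30 PASI score filled by LOCF and "missing PASI 75, PASI 90 and PASI 100 response at week 30 imputed by NRI". SAP 9.6.3 applies LOCF to BSA and NRI to sPGA 0/1 at week 30. SAP 9.6.2.2 repeats the PASI models on observed data.

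**The concern.** The Week 30 row mixes two clocks. The dose-anchored target only chooses among visits already inside the window; it cannot bring in one that falls outside. If the week-28 dose is late enough, a PASI taken on schedule relative to that dose lands on day 211 or later and has no efficacy visit to belong to.

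A response that was observed would then be scored as a non-response, and an observed PASI or BSA would be overwritten. The last scheduled efficacy assessment before week 30 is at week 20. For the switching group that is before the final five ABP 501 doses (weeks 20, 22, 24, 26 and 28), so the substitute says nothing about the last switch. The observed-data models would lose the record too, so no planned week-30 efficacy analysis recovers it. Dose delays are tied to infections and adverse events, so the loss would not be random.

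**Working it through.** **Reproducing the plan's figures.** SAP 5.1 defines "On or After Study Day 1: Study Day = (Date of assessment – Date of Study Day 1) +1". Target day = 1 + 7 × (week − 1):
- Week 28: 1 + 7 × 27 = 190, as stated.
- Week 32: 1 + 7 × 31 = 218, as stated.
- Week 30, nominal: 1 + 7 × 29 = 204.
- Week 30 window length: 210 − 197 + 1 = 14 days, as stated.

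**Week-30 day.** Week-30 day = week-28 dose day + 14 + e, with e from −2 to +2. This borrows the PK tolerance for the PASI done at the same visit. The record is lost to week 30 when the result exceeds 210.

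| Week-28 dose day | Possible week-30 days | Days past 210 |
|---|---|---|
| 187-193 | 199-209 | none |
| 194 | 206-210 | none |
| 195 | 207-211 | 211 (visit at +16) |
| 196 | 208-212 | 211-212 (visit at +15 or +16) |
| 197 | 209-213 | 211-213 (visit at +14 or later) |
| 198 | 210-214 | 211-214 (visit at +13 or later) |

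**Which dose days comply.** There are three readings of the protocol:
- The ±3 days is a hard limit on the dose: 190 ± 3 gives days 187-193, and nothing is lost.
- The 5-day delay counts from the target day: latest dose 190 + 5 = 195. An on-time visit falls on day 209, inside. Only the full 5-day delay plus a visit 2 days late reaches day 211.
- The 5-day delay is added to a visit already 3 days late: latest dose 190 + 3 + 5 = 198. An on-time visit falls on day 212, outside.

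Delays at earlier doses do not shift week 28, because later doses return to the original schedule.

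**Worked case under the third reading.** A subject attends on day 193, is dosed on day 198 after a 5-day delay, and reaches PASI 90 on day 212, exactly 14 days after the dose. SAP 5.1 places day 212 in the Week 32 row. The subject is counted as a non-responder for PASI 75 and 90, and percent improvement is taken from week 20.

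**Scale per subject.** Planned randomization is 342 / 2 = 171 per group. With the 15% loss assumed for PK evaluability, 0.85 × 171 ≈ 145. One responder recoded lowers that group's rate by 1/171 = 0.6 to 1/145 = 0.7 percentage points. The size of the Per-protocol Efficacy Set is not given, so this range is only illustrative.

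**The case against.** The best defence is Table 1-2 footnote a, repeated in SAP 5.1, which applies the ±3 days to the week-28 dose as well as the visit. Read strictly, every compliant week-30 visit falls on days 199-209 and the window works. This stands as far as it goes: if ±3 days is a hard limit, no fully compliant visit is lost. But Table 1-1 footnote i allows a longer delay at dosing visits without excepting week 28, and Protocol 6.7 can hold product for a serious infection. The documents do not settle which governs. The visit rule also applies to every record, compliant or not.

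Four further points have weight:
- Without adding the two allowances together, only one corner case remains (day 195 with a visit at +16).
- The ±48 hours is not stated for PASI.
- A very late dose might be classed as an important protocol deviation and remove the subject from the Per-protocol Efficacy Set, though receiving a dose late is not in itself an exclusion. The FAS observed-data model would still lose the record.
- Efficacy is secondary and, per Protocol 2.1, assessed descriptively; the same rule applies to both randomized groups.

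These limit the importance of the point but do not remove the mismatch.

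**Conclusion.** The point stands in a narrow form. The Week 30 row pairs a moving target with a fixed window, and a genuine week-30 PASI, sPGA or BSA loses its label when the week-28 dose falls on day 195 or later in the combinations shown. The consequences are NRI for PASI 75/90/100 and sPGA 0/1, LOCF for PASI percent improvement and BSA, and loss from the observed-data models.

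A reader might infer more than the documents support:
- **That any delayed dose is misfiled.** Doses through day 194 never are, under a ±2-day visit tolerance.
- **That the record is analysed as week 32.** Week 32 has no efficacy endpoint, so the record has no efficacy visit at all.
- **That PASI percent improvement is missing in the main efficacy analysis.** It is imputed there, and missing only in the observed-data analyses.
- **That the treatment difference is biased by a known amount.** No frequency of late week-28 doses is given, so neither the number affected nor any effect on the between-group difference can be computed. The number is probably small.
- **That the primary PK result is at risk.** AUC and Cmax come from the week 28-30 profile with actual sampling times and do not use this window.

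The correction is worth making because the rule replaces real data in a reachable case and costs little to change.

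**What to change.** In SAP 5.1, assign the nominal day-14 post-dose visit to Week 30 for efficacy, as is already done for PK concentrations in weeks 28-30. Keep the fixed study-day window for subjects without that visit or without a week-28 dose. This works under any reading of the protocol's delay rules.

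At minimum, extend the Week 30 upper bound to day 214 (198 + 16) and start Week 32 at day 215 (218 − 3), the earliest scheduled week-32 day. This covers doses through day 198, but some visits after a longer hold would still be missed.

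A window of 10 to 18 days after the dose is not a good substitute. For a dose on day 190 it accepts only days 200-208, narrower than 197-210. For a dose on day 198 it runs to day 216 and overlaps the week-32 visit.

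Separately, Table 1-1 footnote i, Table 1-2 footnote a and Protocol 6.7 must be reconciled on how the delay and the week-28 window combine.

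The SAP change costs one row of wording and a small edit to the visit-window program. It needs no new data and no protocol amendment.

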5.2 Pharmacokinetic

Pharmacokinetic parameters will be calculated from the serum concentration-time data using noncompartmental methods (Phoenix WinNonlin®, version 8.2 or higher, Pharsight Corp, St. Louis, MO) and actual sampling times. The following PK parameters will be reported:

Variable	Definition
AUC _{tau}	area under the curve from week 28 over the dosing interval up to week 30 using the observed values.
C_{max}	Maximum observed serum concentration obtained directly from the concentration time profile. If multiple maxima occur at equal concentrations, the first temporal value will be taken.
t _{max}	Time at which the maximum serum concentration was observed obtained directly from the concentration time profile
C_{trough}	trough concentration

The AUC $_{tau}$ is the sum of areas up to the dosing interval and will be calculated using the linear trapezoidal rule. AUC $_{tau}$ will be calculated based on actual time post dose for the observed values between week 28 and 30 without extrapolation or interpolation, and estimated up to the last measurable concentration. Individual AUC $_{tau}$ will be flagged and excluded from summary statistics and statistical testing if less than 2 post t_{max} concentration values are reported or less than 2 post t_{max} concentration values are above LLOQ. t_{trough} at a specific week is defined as the pre-dose level for the respective week.

5.3 Efficacy

Body Surface Area (BSA)

Protocol Number: 20200497

Date: 10FEB2023 Page 18 of 36

The percent of BSA affected by Psoriasis (%BSA) is estimated by assuming that the subject's palm, excluding the fingers and thumb, represents roughly 1% of the body's surface (Chandran, 2009).

PASI

The PASI is a measure of the average redness (erythema), thickness (induration), and scaliness (scaling); each graded on a 0–4 scale of the lesions, weighted by the area of involvement (Feldman and Krueger, 2005). PASI combines the assessment of the severity of lesions and the area affected (extent of skin Ps) into a single score in the range 0 (no disease) to 72 (maximal disease).

PASI Percent Improvement from Baseline

PASI percent improvement from baseline is defined as 100 × (value at baseline – value at post-baseline visit) / value at baseline. A percent improvement will not be calculated if the baseline value is missing. A positive value will be considered PASI improvement. Hence, PASI percent improvement will be in a positive direction while PASI percent worsening will be in a negative direction.

PASI Response

PASI Response is defined as a subject meeting or surpassing a pre-specified threshold for percent improvement in PASI score compared to the baseline PASI score. An improvement of at least 75% qualifies a subject as being a PASI 75 responder, an improvement of 90% qualifies a subject as being a PASI 90 responder and an improvement of 100% qualifies a subject as being a PASI 100 responder.

Static Physician's Global Assessment (sPGA)

The sPGA is a 6-point scale (0-5) used to measure the severity of disease (induration, scaling, and erythema). The sPGA should be completed by the same assessor performing the PASI assessments. All assessments for a given subject should be made by the same observer whenever possible.

sPGA Response

An sPGA response is defined as a subject meeting sPGA assessment values of 0 (Clear) or 1 (Almost Clear).

5.4 Safety

Adverse Events Leading to Discontinuation from IP/Study

Protocol Number: 20200497

Date: 10FEB2023 Page 19 of 36

AEs leading to discontinuation from IP/study are those with an action taken with IP indicating "drug withdrawn" or other action taken of "study discontinued".

Event of Interest (EOI)

An EOI is defined as a noteworthy event for a particular product or class of products that a sponsor may wish to monitor carefully. It could be serious or non-serious and could include events that might be potential precursors or prodromes for more serious medical conditions in susceptible individuals (Council for International Organizations of Medical Sciences [CIOMS] VI, 2005). The EOIs for this study will include:

- · Serious infections.
- malignancies,
- hypersensitivity reactions,
- demyelinating disease,
- hematological reactions,
- heart failure,
- lupus-like syndrome,
- liver enzyme elevations,
- and injection site reaction.

The detailed search strategies for the EOIs are included in Appendix A.

Treatment-emergent Adverse Event

Treatment emergent adverse events (TEAEs) during the Lead-in Period are defined as adverse events that start on or after the first dose of IP and prior to the first dose post randomization for randomized and treated subjects, or EOS for lead-in failures or for subjects who were randomized but not treated post-randomization.

TEAEs during the Post-randomization Period are defined as adverse events that start on or after the first dose of IP post-randomization and prior to the EOS.

If the adverse event starts on the same day as the first dose of IP, then the flag indicating whether the adverse event started prior to the first dose on the adverse event CRF page will be used to determine whether this is a TEAE during the Lead-in Period. For randomized and treated subjects, an adverse event that starts on the same day as the first post-randomization dose will be considered as a TEAE post-randomization.

Protocol Number: 20200497

Date: 10FEB2023 Page 20 of 36

6. Analysis Sets

